#### **3.11.1 Adverse Events**

AEs will be coded using the Medical Dictionary for Regulatory Activities (MedDRA) dictionary (Version 20.0 or higher). TEAEs are any AEs occurring or worsening in severity after the first administration of study medication. All AEs (including SAEs) will be graded using the 5-point CTCAE V5.0 scale (mild, moderate, severe, life threatening, or death); their causality with KD025 will be classified into following 5 classes: definitely related, probably related, possibly related, unlikely related, not related. The Investigator will further assess the relationship of adverse events to cGVHD or the underlying disease.

The number and percentage of patients who experienced at least one TEAE as well as the number and percentage of patients who experienced adverse events of each specific system organ class (SOC) and preferred term (PT) will be presented. For the presentation of AE incidences, the SOCs and the PTs within each SOC will be presented by decreasing total

frequency. Tabulation by maximum severity and relationship to KD025 will also be included by treatment group.

TEAEs, Grade  $\geq 3$  TEAEs, SAEs and TEAEs leading to dose modification / discontinuation will be summarized according to treatment arm, system-organ-class, and preferred terms. These analyses will be repeated for events considered related (definitely related / probably related / possibly related) to KD025

Subject listings will be provided for SAEs, AEs resulting in study drug discontinuation and deaths.

AEs will also be presented in listings. Time to onset and duration of AEs will be included in listings, along with action taken and outcome.

### **3.11.2 Adverse events of Note**

AEs of note include:

- Hepatic AEs by CTCAE V5.0 criteria; grouped terms will also be presented.
- Bacterial infection, Viral infection and Fungal infection
- Cytopenias

Those AEs of note will be summarized according to treatment group and preferred terms. Also see Section 3.11.3 for LFT analyses.

### **3.11.3 Clinical Laboratory Evaluation**

The summary statistics (including number, mean, standard deviation, median, minimum and maximum) of all laboratory variables and changes from baseline will be calculated for each visit or study assessment by treatment group. For parameters of WCC, neutrophils (absolute count), lymphocytes (absolute count), monocytes (absolute count), Hb, platelets, ALP, ALT, AST, GGT, total bilirubin, GFR, plots of mean / mean changes from baseline with the corresponding standard error will be displayed.

For shift tables, laboratory results will be classified using the CTCAE V5.0. All graded laboratory parameters will be summarized separately for hematology and biochemistry. Corresponding shift tables to compare baseline to the worst post-baseline grade within the treatment period will be provided.

### **3.11.4 Vital Signs and Other Physical Findings**

Descriptive statistics for vital signs (weight, heart rate, body temperature, systolic and diastolic blood pressure, pulse rate, and respiratory rate) values and the change from baseline will be presented by treatment group for each scheduled assessment time point.

### **3.11.5 ECG**

Descriptive statistics for ECG parameters (i.e., heart rate (HR), PR interval, RR interval, QRS interval, QT interval, and QTcF interval) at each time point with triplicate ECGs will be presented for the values and change from baseline scores (note: Fridericia's correction:  $QTcF = QT/RR^{1/3}$ ).

The number and percentage of subjects with observed QTcF values that satisfy the following conditions will be presented by treatment group and study visit:

- $\leq 450$  ms
- $>450$  to  $\leq 480$  ms
- $>480$  to  $\leq 500$  ms
- $> 500$  ms

The number and percentage of subjects having change from baseline QTcF values that satisfy the following conditions will be presented by treatment group and study visit:

- $\leq 0$  ms
- $>0$  to  $\leq 30$  ms
- $>30$  to  $\leq 60$  ms
- $> 60$  ms

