	
The mITT population is the primary population for the analysis of the primary efficacy endpoint.
 
Data Presentations/Descriptive Statistics
 
Three analyses are planned:
 
1. An IA will be conducted approximately 2 months after 126 participants have been enrolled into the mITT population. A nominal 1-sided alpha of 0.0025 will be spent, but there will be no early study termination for efficacy.2. The primary analysis (PA) will be conducted approximately 6 months after 126 participants have been enrolled into the mITT population, with 1-sided alpha 0.0225 (or 0.025 if the ORRs of both arms are significant at interim).3. A follow-up analysis will be conducted approximately 12 months after 126 participants have been enrolled into the mITT population.4. Additional analyses will be conducted to include adolescent participants and Companion Study participants, approximately 6 months after completion of enrollment of the respective participants. 
Alpha will only be allocated to the primary endpoint, ORR. Demographics, participant disposition, and screening and baseline characteristics will be summarized for the ITT population.
 
AEs will be coded using the MedDRA dictionary (Version 20.0 or greater). The number and percentages of participants experiencing treatment-emergent AEs will be tabulated by system-organ-class (SOC) and preferred term (PT) and will be presented by treatment group. The number of events by preferred term will also be summarized. Tabulation by maximum severity and relationship to treatment will also be included by treatment group. Summary participant listing will be provided for SAEs, AEs resulting in study discontinuation, and deaths.
 
AEs, SAEs, related AEs, related SAEs, Grade ≥ 3 AEs, related Grade ≥ 3 AEs, and AEs leading to withdrawal and treatment discontinuation will be summarized according to treatment group.
 
Laboratory results will be summarized by treatment group. Incidence of laboratory abnormalities will be summarized by treatment group. The worst on-study grade during the treatment period will be summarized. The incidence of \geqGrade 3 laboratory abnormalities under treatment and shifts in toxicity grading from baseline to highest grade post-baseline will be displayed.
 
Vital sign measurements and ECGs will be summarized by treatment group at each scheduled time point using descriptive statistics and included in data listings.

--	---

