6.2 STUDY VISITS

6.2.1 Screening

During screening, participants will have the following completed:

- Provide informed consent / assent.
- Demographic information including gender, age (date of birth), ethnic origin and race.
- Medical history.
- Transplant history including indication for and type of prior transplant(s).
- GVHD history (acute and chronic).
- cGVHD treatment history, including prior therapies and lines of treatment for cGVHD ([Section 4.5](#)).
- Physical examination. All clinically significant findings, either new or worsening throughout the study will be documented as AEs or SAEs.
- Height, weight and body mass index (BMI).
- Seated vital sign measurements (sitting blood pressure, pulse, respiratory rate, temperature).
- Karnofsky (if aged ≥ 16 years) / Lansky (if aged < 16 years) Performance Scale score ([Appendix G](#)).
- Hematology ([Table 4](#)).

- Clinical chemistry ([Table 4](#)).
- Virology.
- Spirometry (FEV1 and FVC) ([Appendix J](#)).
- Supine 12 Lead ECG, single.
- Highly sensitive urine or serum pregnancy test (for females of childbearing potential). Positive urine results are to be confirmed with serum testing.
- Concomitant medications / procedures assessment

Baseline cGVHD severity must be assessed (a stratification factor for randomization). Chronic GVHD severity is defined in [Section 5.3 \(26\)](#).

Eligible participants may be randomized after Medical Monitor approval during the screening window or on C1D1 prior to dosing with belumosudil.

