6.2.4 Cycle 2 and Beyond, Day 1 (± 3 days)

On Day 1 of Cycles 2, 3, 5, 7 and then every other 3 treatment cycles (C10D1, C13D1, etc.), participants will come to the clinic to have the following procedures completed:

Pre-dose

- Concomitant medications / procedures assessment.
- AE assessment.
- Symptom directed PE.
- Highly sensitive urine or serum pregnancy test (for females of childbearing potential). Positive urine results are to be confirmed with serum testing. Refer to [Section 6.4.5](#) for positive serum tests.
- Weight measurement.
- Height and BMI if aged <18 years.
- Seated vital sign measurements (sitting blood pressure, pulse, respiratory rate, temperature).
- Karnofsky (if aged ≥ 16 years) / Lansky (if aged <16 years) Performance Scale score ([Appendix G](#)).
- Hematology ([Table 4](#)).
- Clinical Chemistry ([Table 4](#)).
- Single 12-lead ECG ([Table 10](#)).
 - Single ECG on C2D1, C3D1, C5D1, C7D1 and Day 1 of every 3rd cycle thereafter through C19D1.
 - Starting on C19D1 only if clinically indicated.
- Document corticosteroid dosage.
- Document other cGVHD therapies.
- * Pulmonary function tests ([Appendix J](#)).
 - Can be post-dose.
 - Full PFTs (including FEV₁, FVC, DLCO (corrected for Hb), TLC, and RV) are required after Cycle 2, 6, 12 and every 6th Cycle thereafter (Day 1 of Cycles 3, 7, 13, 19 etc.). At other cycles, spirometry (FEV₁ and FVC) is sufficient.
- * Clinician-Reported Global cGVHD Activity Assessment.
- * Response assessment.
- * cGVHD Activity Assessment - Patient Self Report.
- * Lee cGVHD Symptom Scale ([Appendix D](#)).

- * PROMIS Global Health score ([Appendix E](#)).
- Sparse PK sampling on C2D1 and C7D1 only for all participants ([Table 7](#)).
- Pharmacodynamic sampling on C2D1 and C7D1 only ([Table 9](#)).

Dosing / Post dose

- Study drug administration.
- Dispense / collect study drug.
- Dispense / collect study drug diary.
- Sparse PK sampling on C2D1 and C7D1 only for all participants at 3 hours post-dose ([Table 7](#)).
- For full PK participants, PK sampling 1, 2, 3, 4, 5, 6, 7 and 8 hours post dose with an optional sample at 12 hours post dose on C2D1 only (prior to belumosudil PM dosing for Arm B participants) ([Table 7](#)).
 - Full PK participants should also have C2D2 PK sample drawn prior to dosing.

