11.9 SAFETY ANALYSES

Safety is a secondary endpoint.

Treatment exposure will be summarized.

Safety analyses include:

- Adverse Events and SAEs
 - Treatment-emergent AEs will be summarized by treatment group using MedDRA® (Version 20.0 or greater) System Organ Class (SOC) and preferred term, classified from verbatim terms. The incidence and percentage of participants with at least 1 occurrence of a preferred term will be included. Causality (relationship to study treatment) will be summarized separately.
 - AEs, SAEs, related AEs, related SAEs, \geq Grade 3 AEs, related \geq Grade 3 AEs, and AEs leading to withdrawal, or treatment discontinuation will be summarized overall and by treatment arm. AEs will also be presented in listings. Duration of AEs will be determined and included in listings, along with action taken and outcome.
- Hematological and clinical chemistry parameters using central laboratory
 - Laboratory results will be classified using CTCAE v5.0 and summarized by treatment arm. Incidence of laboratory abnormalities will be summarized. The worst on-study grade after the first dose of study drug will be summarized. The incidence of \geq Grade 3 laboratory abnormalities under treatment and shifts in toxicity grading from baseline to highest grade post-baseline will be displayed.
- Vital signs
 - Change from baseline in systolic blood pressure, diastolic blood pressure and heart rate will be presented.
- 12-Lead ECG
 - Mean and maximum change from baseline in QTc(F) will be derived.

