Cycle 1	Day 1	Single ECG within 60 minutes prior to belumosudil dosing and at 3 hours post dose (\pm 20 minutes)
Cycle 2, 3, 5	Day 1	Single ECG
Cycle 7 and every 3 rd cycle thereafter through C19	Day 1	Single ECG
From C19 onward only if clinically indicated	Day 1	Single ECG
EOT		Single ECG
28-Day Follow Up		Single ECG

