**Table 5: Safety TLFs**

T/F/L	Title	Population
-------	-------	------------

T	Concomitant medications	miITT
L	Concomitant medications	miITT
T	Treatment exposure and compliance	miITT
L	Treatment exposure and compliance	miITT
T	Dose modifications and interruption	miITT
L	Dose modifications and interruption	miITT
T	Overall summary of TEAEs	Safety
T	TEAEs by Soc/PT	Safety
T	TEAEs by PT	Safety
T	TEAEs by severity and PT	Safety
T	Treatment related AEs by PT	Safety
T	Serious TEAEs by Soc/PT	Safety
T	Serious TEAEs by PT	Safety
T	Treatment related SAEs by PT	Safety
T	Grade 3-5 TEAEs by Soc/PT	Safety
T	Grade 3-5 TEAEs by PT	Safety
T	Treatment related grade 3-5 AEs by Soc/PT	Safety
T	TEAEs leading to Study treatment discontinuation by Preferred Term	Safety
T	Related TEAEs leading to Study treatment discontinuation by Preferred Term	Safety
T	TEAEs leading to dose interruption by Preferred Term	Safety
T	Related TEAEs leading to dose interruption by Preferred Term	Safety
T	TEAEs leading to dose modification by Preferred Term	Safety
T	Related TEAEs leading to dose modification by Preferred Term	Safety
T	TEAEs leading to dose reduction by Preferred Term	Safety
T	Related TEAEs leading to dose reduction by Preferred Term	Safety
L	AEs	Safety
L	AE Leading to treatment discontinuation	Safety
L	Death	Safety
T	Lab values and their change from baseline	Safety
F	Lab values by visit	Safety
T	Shifts in CTC grade from baseline to highest grade post-baseline of laboratory	Safety
L	Lab values with CTC grade $\geq 3$	Safety
T	Vital signs and their change from baseline	Safety
L	Vital signs	Safety
T	ECG parameters and their change from baseline	Safety

F	ECG parameters by visit	Safety
T	Number and percentage of subjects with QTcF by visit a) absolute ranges and b) change from baseline	Safety
T	QTcF abnormalities	Safety
L	ECG values	Safety

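### SAP 3.11.5 limits ECG descriptive statistics to triplicate-ECG time points, a kind of time point that the current protocol no longer contains

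*SAP*

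**What the plan says.** **SAP.** Section 3.11.5 gives descriptive statistics for heart rate and the ECG intervals, including QTcF, as values and as change from baseline, but only "at each time point with triplicate ECGs". The same section then plans two categorical tables without that condition. One classifies observed QTcF values; the other reports "The number and percentage of subjects having change from baseline QTcF values that satisfy the following conditions". Both are by arm and visit. Table 5 (Safety TLFs) lists "ECG parameters and their change from baseline" for the safety population, an ECG figure by visit, a QTcF abnormalities table and an ECG listing. None of these titles mentions triplicates.

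**Protocol.** All ECGs are single:

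- Screening (6.2.1): "Supine 12 Lead ECG, single".
- Cycle 1 Day 1 (Table 10): "Single ECG within 60 minutes prior to belumosudil dosing and at 3 hours post dose".
- Cycle 2 onward (6.2.4): "Single ECG on C2D1, C3D1, C5D1, C7D1 and Day 1 of every 3rd cycle thereafter through C19D1".
- End of treatment and 28-day follow-up (6.2.5, 6.2.6 and Table 10): also single.

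On analysis, the synopsis states: "Vital sign measurements and ECGs will be summarized by treatment group at each scheduled time point using descriptive statistics". Section 11.9 adds: "Mean and maximum change from baseline in QTc(F) will be derived". Section 6.4.1 names the same two quantities as safety endpoints.

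**The concern.** The SAP selects time points by a kind of measurement that the current protocol does not make. A programmer who follows 3.11.5 would leave single-ECG visits out of the mean-change table, although the data have been collected and the protocol says they will be summarised. A programmer who follows the Table 5 titles would include them. A SAP should not leave that choice open, least of all for a QTc summary.

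The filter is specific to ECGs. The neighbouring sections on laboratory data (3.11.3) and vital signs (3.11.4) summarise every visit or scheduled assessment.

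A second, smaller gap concerns the maximum change named in Protocol 11.9. The SAP does not say whether this is the largest change among participants at a visit or each participant's own largest change after baseline.

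**Working it through.** The plan states no figure on this point, so there is nothing to reproduce. The check is a count of time points followed by a comparison of the relevant sections.

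**Step 1. Count the ECG time points in the current schedule** (Protocol 6.2.1, 6.2.2, 6.2.4 to 6.2.6 and Table 10):

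- Screening: 1
- Cycle 1 Day 1, pre-dose and 3 hours post-dose: 2
- Day 1 of Cycles 2, 3 and 5: 3
- Day 1 of Cycles 7, 10, 13, 16 and 19: 5
- End of treatment and 28-day follow-up: 2

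Total: 1 + 2 + 3 + 5 + 2 = 13. Table 10 places Cycle 19 both in the routine series and in the period when ECGs are done on clinical indication only. Without Cycle 19 the total is 12. Taking screening and Cycle 1 pre-dose as the two pre-treatment readings, 13 − 2 = 11 time points (or 12 − 2 = 10) can carry a change from baseline.

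**Step 2. Apply the SAP condition.** Time points specified as triplicate: 0. The descriptive summary in 3.11.5 therefore covers 0 of 12 to 13 time points under the current schedule, and the change summary 0 of 10 to 11. Without the triplicate condition, both would cover all of them.

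**Step 3. Compare the places that govern the ECG summary.**

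| Place | Time points summarised | Triplicate condition |
|---|---|---|
| SAP 3.11.5, descriptive statistics | Triplicate time points only | Yes |
| SAP 3.11.5, categorical QTcF tables | Each study visit | No |
| SAP Table 5, ECG change table and figure | Figure by visit; table title does not say | No |
| Protocol synopsis | Every scheduled time point | No |
| Protocol 11.9 and 6.4.1 | Mean and maximum QTc(F) change; time points not specified | No |

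Only one of the five carries the restriction.

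**Step 4. Look for evidence on earlier schedules.** The summary of changes for the current amendment says that triplicate text was removed, so earlier versions had some triplicates. The Amendment 2 log (Appendix O, 21.15.2) describes the ECGs from Cycle 7 Day 1 onward as single even then. This suggests that earlier schedules mixed the two types, in which case the filter would also drop the later visits of earlier participants. The earlier schedule itself is not in the documents, so these visits cannot be counted.

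**Step 5. Check the maximum.** SAP 3.14 includes the maximum among the default statistics for continuous data. Applied to change from baseline by visit, it gives the largest change among participants at that visit. It does not give the distribution of each participant's largest post-baseline change. SAP Table 5 lists a QTcF abnormalities table but does not define its content.

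**The case against.** The strongest reply is that the phrase was sensible when written. The SAP history ties version 2.0 to Amendment 1, and the SAP describes 126 subjects. Triplicates were removed only with the current amendment, so the condition probably selected real visits. Amendment 3 expected participants other than the 20 adolescents to leave the study once they had at least 6 months of treatment, so the analyses of the 126 rest largely on ECGs taken under earlier versions. Restricting mean QTcF summaries to triplicates can also be defended on precision.

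Much of this stands, and it rules out three stronger readings:

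- *A reader might infer that no mean QTcF change would be reported at all.* The documents do not support this. Earlier participants may have qualifying visits, and SAP Table 5 commits to an ECG change table and by-visit figure without the condition. The SAP contradicts itself; it does not drop the summary outright.
- *A reader might infer that the maximum change is missing from the SAP.* The default statistics in 3.14 supply a maximum wherever change is summarised. Only a per-participant maximum is undefined, and Protocol 11.9 does not say explicitly that this is what it means.
- *A reader might infer that this phrase is what keeps later adolescents out of the ECG tables.* The SAP plans three analyses timed from the 126th subject and does not describe the additional adolescent analyses in Protocol 11. That gap is wider than the ECG wording.

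The history explains the mismatch but does not resolve it. If precision was the reason for the filter, the SAP does not say so, and the protocol makes no such exception.

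**Conclusion.** The point holds as an inconsistency to reconcile. SAP 3.11.5 applies a condition that no time point in the current protocol meets (0 of 12 to 13 through Cycle 19). It disagrees with the synopsis, with Protocol 11.9 and with SAP Table 5. Read literally, it removes from the mean-change summary every visit under the current schedule and any single-ECG visit under earlier versions.

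The effect is limited. The categorical QTcF tables and the ECG listing are untouched, no data are lost, and nothing about the overall response rate or its alpha is involved. The number of participants and earlier visits affected cannot be stated, because neither the earlier ECG schedule nor the number assessed under the current one is given.

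The conclusion assumes that this SAP, or its ECG wording, will be used for data collected under the current protocol; no other SAP is supplied. The part about earlier single-ECG visits rests on the amendment logs alone. This is a minor correction that is worth making.

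**What to change.** In SAP 3.11.5, replace the triplicate condition with: *at each scheduled ECG time point, using the single reading, or the mean of the triplicate where one was taken under an earlier protocol version*. The averaging rule is needed in any case, because 3.11.5 gives none. The text would then agree with SAP Table 5 and the protocol synopsis.

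Add one sentence stating that the maximum change in Protocol 11.9 is each participant's largest post-baseline QTcF change from baseline, summarised by arm.

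The cost is about two sentences and some programming, with no new data. The downside is small: single readings are more variable than triplicate means, so a table that mixes them has uneven precision. A footnote giving the number of single and triplicate readings at each visit would make this visible.

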### **3.11.6 Physical Examination**

Clinically significant physical examination findings will be captured as AEs.

## **3.12 Pharmacokinetic Analysis**

Further details will be described in the Pharmacokinetic Analysis Plan.

### **3.13 Pharmacodynamics Analysis**

Further details will be described in the Pharmacodynamics Analysis Plan.

### **3.14 General Methods**

#### **Computing Environment**

All statistical analyses will be performed using SAS® Version 9.3 or higher for Windows.

#### **Reporting of Numerical Values**

Continuous data will be described using descriptive statistics: number of observations (n), mean, standard deviation, median, minimum and maximum. Frequencies and percentages will be used for summarizing categorical data. When categorical data are presented, the percent will be suppressed when the count is zero in order to draw attention to the nonzero counts. The denominator for all percentages, unless otherwise specified, will be the number of subjects in the specified analysis population or group.

Means, medians, standard deviations, and confidence intervals will be reported to one decimal place more than the data reported on the case report form (CRF) or by the laboratory/vendor. Minimum and maximum will be reported to the same number of decimal places displayed on the CRF or by the laboratory/vendor. P-values will be reported to 4 decimal places.

